10.6 Exploratory Objectives

Identify predictive patterns of blood biomarkers which identify patients at high-risk of developing clinically significant osteonecrosis.

Associations between the blood biomarkers and CTCAE grade 2 or higher ON will be analyzed using mixed-effect logistic regression models.

Identify MRI findings during late induction which correlate with osteonecrosis lesions seen during reinduction.

The MRI finding during late induction is represented by a 3-level ordinal variable (none, small, large). The ON lesions seen during reinduction are represented by a binary variable (large, less than large). The association will be tested by the Chi-square test on a 3-by-2 contingency table with ordered rows.

Compare induction blood pressure control and intervention arm to echocardiographic changes at reinduction II.

Echocardiographic changes at reinduction II is measured by the LV strain which is a continuous variable. Comparison of the LV strain between the intensive BP treatment and standard care arms will be performed by Wilcoxon rank-sum test.

Evaluate patient-reported, health-related quality of life in patients during induction and after 1.5 years of therapy when many experience the symptoms of osteonecrosis.

Survey response scores will be summarized by descriptive statistics including mean, standard deviation, minimum, maximum, quartiles, range and inter-quartile range.

Time frame: The analysis will begin within 6 months after the MRI assessments of the last randomized patient is completed, except for the last exploratory objective for which the analysis will begin within 6 months after the last randomized patient is followed for 1.5 years after completion of chemotherapy.

Responsible investigators: [name], [name]

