1.3 Exploratory Objectives

- 1.3.1 Identify predictive patterns of blood biomarkers which identify patients at high-risk of developing clinically significant osteonecrosis.
- 1.3.2 Identify MRI findings during late induction which correlate with osteonecrosis lesions seen during reinduction.
- 1.3.3 Identify patterns of diurnal blood pressure variation as measured by ambulatory blood pressure monitoring associated with the later development of osteonecrosis.
- 1.3.4 Compare induction blood pressure control and intervention arm to echocardiographic changes at reinduction II.
- 1.3.5 Evaluate patient-reported, health-related quality of life in patients during induction and after 1.5 years of therapy when many experience the symptoms of osteonecrosis.

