2.0 BACKGROUND AND RATIONALE

2.1 Background

Advancements in the treatment of acute lymphoblastic leukemia (ALL) have pushed the cure rate to greater than 90%.¹ Intensifying glucocorticoid use (i.e. prednisone and dexamethasone) has been key in accomplishing these outcomes. However, glucocorticoid-induced osteonecrosis (ON) is one of the most common dose-limiting toxicities of ALL therapy in children.²⁻⁶ Symptomatic cases (defined as Common Terminology Criteria for Adverse Events (CTCAE) grade 2-4) often occur during the first two years of treatment, and may result in early discontinuation of glucocorticoids from treatment. Age is the most significant risk factor, with ALL patients greater than 10 years of age at higher risk of developing ON.^{2,3,5,6} The most common affected joints are the hip, knee, and shoulder.⁷⁻⁹ In both Total XV³ and Total XVI¹⁰, the rate of symptomatic osteonecrosis in children age 10 or older was ~40%.

Recent work has demonstrated that patients with ALL age 10 or older at diagnosis who develop hypertension during glucocorticoid containing phases of therapy were more likely to develop osteonecrosis. Among 235 children treated on Total XV and Total XVI, osteonecrosis occurred in 52% of the 94 who developed hypertension compared to 38% of those who were normotensive [p=0.037, odds ratio (OR) 1.75, 95% confidence interval (95% CI) 1.02-3.01].¹¹ The association was maintained in a multivariable analysis of all known factors associated with either hypertension or osteonecrosis (p=0.03, OR 1.88, 95% CI 1.1-3.22). When the analysis was restricted to osteonecrosis that developed during protocol therapy, 52% of patients with hypertension developed osteonecrosis compared to 34% of normotensive patients (p=0.006, OR 2.11, 95% CI 1.2-3.6). Hypertension was also associated with an increased frequency of extensive epiphyseal involvement ($\geq 30\%$ of the surface effected) of the hip and knee joints on screening MRIs; this is significant as this degree of involvement is associated with joint collapse and the need for surgical intervention.^{12,13}

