2.2 Rationale

Based on the retrospective clinical and prospective preclinical data, undertreatment of hypertension is associated with an approximately 2-fold increased risk of developing osteonecrosis after accounting for other known risk factors. Data from both adult^{14,15} and pediatric¹⁶ populations shows a benefit to more intensive blood pressure control compared to conventional control. Due to the risks of complications from untreated hypertension (e.g. posterior reversible encephalopathy syndrome), it is both impractical and unethical to randomize patients to no treatment for their hypertension. We will therefore test the efficacy of intensive hypertensive control (targeted to the 50-75th

percentile for age, sex, and height, systolic) compared to conventional antihypertensive control (targeted to the 90-95th percentile for age, sex, and height, systolic). We have chosen slightly higher systolic blood pressure goals for the intensive arm compared to the ESCAPE trial¹⁶ due to the presence of anemia and risk for infection in pediatric ALL patients, both of which may predispose to an increased risk of symptomatic hypotension.

The Children's Oncology Group AALL0232 and CCG1961 trials demonstrated differences in osteonecrosis in patients receiving dexamethasone instead of prednisone during induction, or continuous instead of alternate week dexamethasone during delayed intensification, respectively.^{2,5} These data support the critical role that these two steroid-intensive phases of therapy (termed induction and reinduction in St. Jude Total Therapy protocols) play in the development of osteonecrosis. The planned intervention will therefore encompass these two periods.

Although TOT17 includes an optional randomization for vincristine and dexamethasone duration (49 weeks vs. 101 weeks), the primary endpoint in this study (Reinduction II MRI) occurs prior to that randomization. Thus, the randomization will not impact the primary outcome of the study. Furthermore, review of symptomatic osteonecrosis timing on TOTXVI suggests that the majority of patients develop symptoms prior to this timepoint. For secondary endpoints including CTCAE symptomatic osteonecrosis, we will consider dexamethasone duration as a covariate.

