5.2 Evaluations during Therapy

Evaluation	Timing during Induction	Timing post-Induction
Ambulatory blood pressure monitoring (ABPM)	Once for 12-30 hours on day 4-7, once for 12-30 hours on day 23-28	-
Magnetic resonance imaging of hip and knee	Once during Days 23-28#	Reinduction 2 per Total 17 protocol
Vasomotor testing (arterial elasticity, pulse wave velocity) #	Once during Days 23-28	Once between Early Intensification day 57 and Consolidation day 28, (optional) once Continuation week 120 ±2 weeks
Serum for vascular biomarkers ^{&}	Day 22 +/- 2 days	Week 17 of Continuation (Reinduction II)
Echocardiogram		Once during week 17-19 of Continuation (Reinduction II)#
Symptom survey (PROMIS: Ped 25 Profile, Pain interference 8a, Physical activity 8a, Mobility 8a)	Once on day 23-28	Week 17 of Continuation (Reinduction II) ± 2 weeks, week 49 ± 3 weeks
Semi-structured interview of treatment and symptom burden #		Week 49 ± 3 weeks (with symptom survey)

All days/ weeks refer to the date of Total 17 therapy (i.e. day 22 refers to day 22 of Total 17, not the 22nd day since HYPERION entry or randomization).

***The St. Jude IRB requires that a female patient of childbearing potential must have a negative pregnancy test as a condition of clinical research eligibility.*

SJCRH Memphis patients only

& See HYPERION Manual of Operations for collection, processing and shipping instructions.

Obtain other studies as needed for good patient care and per the TOT17 protocol.

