10.4 Primary Objective

To compare the frequency of radiographically significant osteonecrosis in patients receiving intensive compared to conventional antihypertensive therapy.

The primary endpoint is the number of major joints (hips and knees) with extensive epiphyseal osteonecrosis ($\geq 30\%$ affected surface^{12,13,17}) on MRI after approximately 9 months of chemotherapy (during reinduction 2). All randomized patients with appropriate imaging are considered evaluable and all analyses will be done according to intent-to-treat.

A chart review of 140 TOTXVI patients meeting the eligibility criteria of this study showed the following distribution of the number of affected joints in the low BP within-target group vs. the above-target group:

	Number of affected joints					Total
	0	1	2	3	4	
Above-target (proportion, n)	0.583, 70	0.083, 10	0.233, 28	0.017, 2	0.083, 10	120
Within-target (proportion, n)	0.80, 16	0.05, 1	0.10, 2	0.00, 0	0.05, 1	20

Clearly in each BP group the distribution is bi-modal with local modes at 0 and 2.

The primary analysis will consist of two parts. In the first part the distribution of the number of affected joints will be compared by the exact one-sided Chi-square test comparing the probability of having at least 1 affected joint. Let $P_0(k)$ and $P_1(k)$ be the probability of k affected joints among patients above- and within-target respectively ($k=0,1,2,3,4$). We have noted in the preliminary data that the BP of 14.6% of the eligible patients was within target without any treatment. Therefore, the distribution of the number of affected joints in the control group is anticipated to be $PC(k)=0.854*P_0(k)+0.146*P_1(k)$, and the distribution in the treatment group is anticipated to be $PT(k)=P_1(k)$, $k=0,1,2,3,4$. Applying the preliminary data displayed above to this model, we obtain the anticipated distribution in the control and treatment group as follows:

	Number of affected joints k	
	0	1+
Control	0.615	0.385
Treatment	0.8	0.2

With $n=80$ subjects per group, the one-sided test has the exact power of 78.7% to detect the above anticipated difference at the 5% significance level. The power is calculated using Cytel Studio II.

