10.8 Summary of Primary and Secondary Objectives

Objective#	Objective Type	Analysis#	Resp Party	Stat	Safety	Analysis Measure	Analysis Title	Data Collection Time Frame	# of Participants
1.1.1	P	1	SEK	CC	N	Patient	Intensive vs. conventional hypertension control effect on osteonecrosis	Time on therapy	160
1.2.1	S	2	SEK	CC	N	Patient/ Joint	Antihypertensive intervention patients over time	Time on therapy/ Reinduction II	160
1.2.2	S	3	SCK/CM	CC	N	Patient/ Joint	Antihypertensive treated patients vs. historic control	Time on therapy/ Reinduction II	160
1.2.3	S	4	ND	CC	N	Patient	Blood pressure achieved by intervention arm	Through reinduction II	160
1.2.4	S	5	CM	CC	N	Patient	Induction MRI	Induction	80
1.2.4	S	6	DM	CC	N	Patient	Vascular function by vasomotor testing	Induction, consolidation, off therapy	80
1.2.4	S	7	SEK	CC	N	Patient	Blood markers of vascular dysfunction	Induction, reinduction II	160
1.3.1	E	7	SEK	CC	N	Patient	Blood markers of osteonecrosis risk	Induction, reinduction II	160
1.3.2	E	3/5	SCK/CM	CC	N	Patient	Early vs late MRI findings of osteonecrosis	Induction, Reinduction	80
1.3.3	E	8	ND	CC	N	Patient	ABPM blood pressures vs osteonecrosis	Induction	160
1.3.4	E	7	GB	CC	N	Patient	Echo changes at reinduction vs induction blood pressure	Reinduction II	80
1.3.5	E	9	EK	CC	N	Patient	HRQoL and symptom survey	Induction, reinduction II, week 49	160
1.3.5	E	10	EK	NA	N	Patient	Narrative symptom description	Week 49	80

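### The mixed-effect logistic model for predictive biomarkers (Section 10.6) names no random-effect unit, cannot be estimated on its most natural reading, and does not separate samples taken before osteonecrosis onset from those taken after it

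*Combined protocol and SAP*

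**What the plan says.** Objective 1.3.1 (Section 1.3) is to "Identify predictive patterns of blood biomarkers which identify patients at high-risk of developing clinically significant osteonecrosis". The whole analysis plan is one sentence in Section 10.6: "Associations between the blood biomarkers and CTCAE grade 2 or higher ON" "will be analyzed using mixed-effect logistic regression models". No grouping unit, random-effect structure, covariate set or choice of sample follows.

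The rest has to be pieced together from other sections:

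- **Samples.** Section 5.2 schedules serum for vascular biomarkers at day 22 (± 2 days) of induction and at week 17 of continuation, which is Reinduction II.
- **Unit.** Table 10.8 lists the analysis titled "Blood markers of osteonecrosis risk" with the patient as the measure, induction and reinduction II as the time frame, and 160 participants. Objectives 1.2.1 and 1.2.2 in the same table carry a combined patient/joint measure.
- **Calendar.** Section 10.4 puts the Reinduction II MRI about 9 months into chemotherapy.
- **Onset of symptoms.** Section 2.1 says symptomatic cases "often occur during the first two years of treatment" and gives a rate of about 40% at age 10 or older. Section 2.2 reports from a review of TOTXVI that "the majority of patients develop symptoms prior to this timepoint".
- **Dates.** Section 8.2 lists the onset date among the adverse-event items recorded.

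**The concern.** There are two separate problems.

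**The model.** A mixed-effect model earns its random effect when the response is repeated within a cluster. The plan's only other mixed model (blood pressure, Section 10.5) is of that kind, because the response is measured repeatedly in each patient. For objective 1.3.1 it is the predictor that is measured twice, while the outcome is a single yes/no. Stacking the two samples copies that outcome into two rows that always agree, and a patient random intercept then has nothing to estimate.

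**The time order.** The aim is prediction, but one of the two samples is drawn around month 9, when some patients may already have symptomatic osteonecrosis. No section excludes samples taken after onset or confines prediction to day 22. A marker that rises because bone is already affected could be reported as one that identifies patients at risk, and could then be carried into later risk-stratification work.

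**Working it through.** The documents give no power, sample size or error rate for objective 1.3.1, so there is no figure of the plan's own to reproduce.

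**1. Patient random intercept with one outcome per patient.** Three datasets were simulated, each with 160 patients (table 10.8), two marker values per patient with correlation 0.5 (assumed), and one outcome driven by the day-22 marker with a log odds ratio of 0.6 per SD (assumed). The random-intercept likelihood was maximised at fixed values of the random-effect SD, σ. The population-averaged effect is the conditional coefficient divided by √(1 + 0.346σ²). Results for one dataset (56 events):

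| σ | Log-likelihood | Conditional coefficient | Population-averaged |
|---|---|---|---|
| 0 | -203.5 | 0.37 | 0.37 |
| 3 | -140.8 | 0.53 | 0.26 |
| 10 | -115.1 | 0.72 | 0.12 |
| 30 | -107.4 | 0.84 | 0.047 |
| 100 | -104.7 | 0.90 | 0.015 |

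The other two datasets behave the same way (-206.0 to -105.3, and -212.0 to -111.5). There is no maximum within the range tried. The reason is visible in the first dataset. As σ grows, the model comes to predict that the two rows agree, and the log-likelihood climbs towards that of an intercept-only model with one row per patient: 56 × ln(56/160) + 104 × ln(104/160) = -58.8 - 44.8 = -103.6. The marker contributes almost nothing at that end, and its reported coefficient depends on where the software stops. Ordinary logistic regression of the same outcomes on the day-22 marker gave finite estimates: 0.71 (SE 0.20), 0.31 (SE 0.17) and 0.64 (SE 0.17).

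**2. Week-17 samples after onset.** In 600 simulated trials per setting, a marker had no predictive effect but rose by a fixed amount after onset. It was tested by one-row-per-patient logistic regression at two-sided 5%, N = 160. The 40% rate is from Section 2.1. The 20% rate, the share of cases with onset before week 17 and the size of the rise are assumptions.

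| Share of cases before week 17 | Significant at week 17, 40% osteonecrosis (rise 0.5 SD; 1 SD) | Same, 20% osteonecrosis |
|---|---|---|
| 0% | 5.5%; 6.2% | 5.2%; 4.2% |
| 25% | 11.5%; 31.2% | 8.8%; 22.7% |
| 50% | 32.5%; 85.8% | 25.8%; 66.5% |
| 75% | 66.0%; 99.5% | 47.0%; 93.2% |

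The day-22 test stayed between 2.7% and 6.5% throughout. The distortion comes from the time order, since this model has no random effect at all.

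**3. What the day-22 sample can deliver.** Approximate power = Φ(ln(OR) × √(N p(1 - p)) - 1.96), with OR per SD of the marker (assumed values) and all 160 patients sampled. For p = 0.40, √(160 × 0.40 × 0.60) = 6.20, giving 71%, 93% and 99% for OR 1.5, 1.75 and 2.0. For an assumed p = 0.20, √25.6 = 5.06, giving 54%, 81% and 94%.

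**The case against.** Section 10.6 does not specify a patient random effect or stacked rows, so step 1 tests one construction among several. A site effect would be estimable, and so would joints within patient. Osteonecrosis status could also be scored at each sampling time. The patient label in table 10.8 does not settle the row structure either: objective 1.2.3 carries the same label and is analysed with repeated measurements. The objective is exploratory, and the day-22 samples and onset dates let an analyst order samples against onset without new data.

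Much of this stands. The unit is unstated, and a reader might infer that the study cannot find predictive biomarkers. The documents do not support that, because step 3 shows fair power at day 22. The alternatives do not remove the point, however. No site random effect appears anywhere in the plan. Table 10.8 marks joint-level analyses as such and does not do so here. Status at each sample would test concurrent association, not prediction. None of these choices addresses samples taken after onset.

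A reader might also infer an inflated type I error by treating the two rows as independent. The plan proposes no such analysis, so no such figure is claimed.

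**Conclusion.** The point holds as a defect of specification and time order. On its most natural reading the planned model yields no finite random-effect variance and no usable marker effect. On every reading the plan lets week-17 samples taken after onset count as prediction.

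The size of the second problem depends on a share that the documents do not give. It is tempting to derive one by spreading onset evenly over therapy, but nothing in the protocol supports that. The TOTXVI sentence in Section 2.2 is ambiguous: its timepoint may be the Reinduction II MRI, in which case more than half of cases come first, or the later dexamethasone randomization, in which case the share before week 17 is unknown. The percentages in step 2 are therefore illustrations. Section 2.3 says the link between these markers and osteonecrosis risk is unknown, so week-17 values may reflect existing disease; it is not established that they do.

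This is a minor point. It concerns an exploratory objective, and the primary result does not depend on it.

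**What to change.** Replace the sentence in Section 10.6 with two analyses, each with one row per patient.

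1. **Day 22.** Logistic regression of later grade 2 or higher osteonecrosis on the day-22 biomarkers, excluding any onset before the sample. Section 10.6 starts the analysis within 6 months of the last MRI, and Section 10.1 expects accrual over 3.5 years, so follow-up will differ between patients. Use a fixed horizon or a time-to-onset model.
2. **Week 17.** A landmark analysis of patients free of grade 2 or higher osteonecrosis at that sample, counting only later onsets.

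If a random effect is still wanted, name its unit and the reason for it.

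The cost is SAP wording. Onset dates are already an adverse-event item. Section 9.1 limits adverse-event capture to 4 weeks after removal from treatment, so the text should confirm that osteonecrosis onset dates from the TOT17 follow-up (Section 5.5) will be used.

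The downside is fewer events in the landmark analysis. With 0.40 × 160 = 64 cases and an assumed 25%, 50% or 75% before week 17, there remain 48 events in 144 patients, 32 in 128 or 16 in 112. By the formula in step 3, N p(1 - p) is 32.0, 24.0 or 13.7, and power at OR 1.5 per SD is about 63%, 51% or 32%, against 71% for the day-22 analysis.

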6.0 EVALUATION CRITERIA

6.1 Response Criteria

All patients will be evaluated clinically and radiographically for the development of osteonecrosis. Patients with radiographic (MRI or plain film x-ray) findings of osteonecrosis will be assessed for symptoms by the treating physician or designee. CTCAE version 4 criteria will be used to categorize the severity of osteonecrosis. MRI imaging will be centrally reviewed by a radiologist blinded to treatment assignment to assess the involvement of epiphyseal surfaces (0, <30%, ≥30%) which will be determined for each effected joint.

Blood pressures for each patient will be documented in the research database as the median of each week during induction and the median of each post-induction phase.

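### The patient-level test for objective 1.3.2 cannot separate same-joint prediction by induction MRI from general patient susceptibility; a joint-matched analysis should be added

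*Combined protocol and SAP*

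**What the plan says.** Objective 1.3.2 (Section 1.3) is to "Identify MRI findings during late induction which correlate with osteonecrosis lesions seen during reinduction". It does not say whether the correlation is meant by joint or by patient.

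Section 10.6 gives the analysis in three sentences. The early variable: "The MRI finding during late induction is represented by a 3-level ordinal variable (none, small, large". The late variable: "The ON lesions seen during reinduction are represented by a binary variable (large, less than large". The test: "The association will be tested by the Chi-square test on a 3-by-2 contingency table with ordered rows". There is no joint index, no matching of joints, no term for several joints in one patient, and no rule for reducing several joints to one value.

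The summary table in Section 10.8 lists this analysis as "Early vs late MRI findings of osteonecrosis", with Patient as the analysis measure and 80 participants. Objectives 1.2.1 and 1.2.2 in the same table carry the measure Patient/Joint.

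The joint-level data are planned. Section 5.2 schedules MRI of hip and knee in late induction and at Reinduction II. Section 6.1 has central review "to assess the involvement of epiphyseal surfaces (0, <30%, ≥30%) which will be determined for each effected joint". Section 10.4 counts affected hips and knees, from 0 to 4 per patient.

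**The concern.** A lesion sits in a joint. Once each patient is reduced to one early and one late value, a patient with a small hip lesion at induction and a large knee lesion at reinduction falls in the same cell as a patient whose two lesions are in the same hip. Two explanations of a positive table then look alike: the early finding marks the joint that will deteriorate, or it marks a patient prone to osteonecrosis in any joint.

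The two have different meanings for a reader of the result. The first says something about the early lesion. The second says the scan is one more marker of patient risk. The planned table supports only a statement about patients. If susceptibility varies little between patients, the collapse also dilutes a real same-joint link, because unrelated lesions in other joints blur it.

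**Working it through.** The plan gives no power, significance level or effect size for 1.3.2, so there is no stated figure to reproduce.

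**What one patient contributes.** In a patient-stratified Mantel-Haenszel test, a patient with e early joints, l large late joints and a joints positive at both times contributes a − e·l/4, with variance e(4 − e)·l(4 − l)/(4²·3).
- Early hip lesion, later large knee lesion: e = 1, l = 1, a = 0, so 0 − 0.25 = −0.25.
- Both lesions in the same joint: 1 − 0.25 = +0.75.
- In the patient-level table these two patients are identical.
- A patient with none or all four joints positive at either time has variance 0 and contributes nothing.

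**Is within-patient clustering plausible?** Section 10.4, above-target group (n = 120; 70, 10, 28, 2 and 10 patients with 0 to 4 joints):
- Mean = (10 + 56 + 6 + 40)/120 = 0.933 joints, or 0.233 per joint.
- Independent joints would leave (1 − 0.233)⁴ = 0.35 of patients unaffected; 70/120 = 0.58 were.
- Variance = 300/120 − 0.933² = 1.629, against a binomial 4 × 0.233 × 0.767 = 0.716. The implied intra-patient correlation is (1.629/0.716 − 1)/3 ≈ 0.43.

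Some of this may be left-right pairing (the plan notes modes at 0 and 2), but clustering is clear in the plan's own data.

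**Simulation 1 (assumed model).** 80 patients (Section 10.8), four joints, 4,000 studies per scenario. Logit of an early finding = −2.9 + u; logit of a large late lesion = −2.1 + u + β × early finding in the same joint; u is normal with mean 0 and the SD shown. Assumed: worst-joint collapse, half of early findings large. The patient-level test is the ordered-row (trend) chi-square; the joint-matched test is the Mantel-Haenszel test above; both are two-sided at 5%.

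| Scenario | Patient-level test | Joint-matched test |
|---|---|---|
| β = 0, SD 0.5 | about 9% | about 5% |
| β = 0, SD 1.0 | about 44% | about 5% |
| β = 0, SD 1.5 | about 86% | about 5% |
| β = 1.5, SD 0 to 0.5 | 25–41% | 58–63% |
| β = 1.5, SD 1.5 | about 99% | about 79% |

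Random draws move these by a few points (8–9%, 40–44% and 85–88% in the first three rows). When early and late findings are unrelated even at patient level, the patient-level test rejects in about 4.9%.

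**Simulation 2 (late counts from Section 10.4).** Late joint counts follow the average of the two anticipated arm distributions, so (0.385 + 0.20)/2 = 29.3% have at least one large joint. Assumed: 30–50% of late lesions visible early, 2–5% background early findings per joint.
- Same-joint link: 95–100% (patient-level) against 88–100% (joint-matched).
- Link through the patient only: 95–100% against about 5%. Of patients positive at both times, 32–33% share no joint.
- No link: about 5% for both.

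**How many patients inform a within-patient estimate?** Under simulation 1, about 6 to 16 of 80. A ceiling from Section 10.4: 0.293 × 80 ≈ 23 patients with a large late joint. The four-joint share is 0.854 × 0.083 + 0.146 × 0.05 = 0.078 in control and 0.05 in treatment, average 0.064, or about 5 patients. That leaves about 18, before requiring early findings in some but not all joints. Section 5.3 limits induction MRI to patients scanned without sedation, so fewer than 80 may have both scans.

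**The case against.** The strongest reply is that the planned test answers the stated objective. Objective 1.3.2 mentions no joint matching. Section 10.8 uses a joint label for other objectives and not for this one. The primary test is also per patient. Whether a patient with an early finding goes on to a large lesion is a coherent question, and the table tests it at the correct level. This stands.

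Several stronger readings are therefore not supported:
- A reader might infer that the analysis cannot tell whether induction MRI predicts later lesions at all. It can, at patient level.
- A reader might take the 86% as a false-positive rate. It is not. The model builds in shared susceptibility, so early findings truly go with late lesions: at SD 1.5, late lesions occur in 70% of patients with an early finding and 32% without. Rejecting there is correct.
- A reader might infer that the trial means to use induction MRI to pick out joints at risk. No section proposes that use.
- A reader might fear a by-joint table tested as if joints were independent. Section 10.8 sets the patient as the unit, so that is not the plan.

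It is also fair that the first simulation fits Section 10.4 only loosely. At SD 1.5 it puts 43% of patients with at least one late joint, against 38.5% and 20% anticipated, and it yields more patients with one joint than with two, the reverse of the historical data. The second simulation uses the plan's own counts and shows the same contrast, so the pattern stands while the exact rates do not.

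**Conclusion.** The point holds as a limit on interpretation, and it is minor. The planned table is a valid test of patient-level association. It cannot distinguish same-joint prediction from patient susceptibility, and Section 10.6 does not say how several joints become one value.

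With no joint-specific link, the patient-level test rejects in about 9% to 86% of studies as the assumed SD runs from 0.5 to 1.5, while the joint-matched test stays near 5%. With a same-joint log-odds effect of 1.5 and SD 0 to 0.5, the patient-level test has 25–41% power against 58–63%. With strong susceptibility the ordering reverses and the patient-level test is the more powerful.

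These rates rest on assumed intercepts, SDs, effect size and worst-joint collapse; the documents give no induction lesion frequency. No primary, secondary or safety conclusion changes.

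**What to change.** Amend Section 10.6 for objective 1.3.2, and the analysis measure in Section 10.8 to match:

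1. Keep the 3-by-2 table as the patient-risk analysis and label it so. State the collapse rule, for example the worst joint at each time, and tie none, small and large to the Section 6.1 grades.
2. Add a joint-matched logistic model: involvement of 30% or more at reinduction on the induction grade of the same joint, fitted by GEE with the patient as cluster.
3. Because the GEE coefficient alone still mixes differences between patients with differences within them, report a within-patient estimate beside it (patient-stratified Mantel-Haenszel or conditional logistic), with its confidence interval and the number of informative patients, as exploratory.
4. Confine any statement about particular joints to items 2 and 3.

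The cost is SAP wording and a little analysis on readings already planned per joint, with no new scans, visits or patients. The drawback is that the within-patient estimate will be imprecise, so it supplements the planned table and does not replace it.
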